4.7.3 Additional safety assessments

4.7.3.1 Laboratory variables, vital signs and electrocardiograms (ECGs)

The following laboratory variables, vital signs and electrocardiogram (ECG) variables will be analyzed. They will be converted into standard international units.

- Hematology:
 - Red blood cells and platelets and coagulation: hemoglobin, hematocrit, red blood cell count, platelet count
 - White blood cells: white blood cell count, neutrophils, lymphocytes, monocytes, basophils, eosinophils
- Clinical chemistry:
 - **Metabolism:** Glucose, total cholesterol, total protein, creatine phosphokinase
 - **Electrolytes:** Sodium, potassium, chloride, calcium, bicarbonate
 - **Renal function:** Creatinine, blood urea nitrogen, uric acid
 - **Liver function:** Alanine aminotransferase, aspartate aminotransferase, alkaline phosphatase, lactate dehydrogenase, total bilirubin, albumin
 - **Pregnancy test:** Serum β -human chorionic gonadotropin (all female participants) will be performed at screening (V1) in women of childbearing potential, and a urine pregnancy test will be performed at V2 and every 4 weeks thereafter
 - **Hepatitis screen:** Hepatitis B surface antigen (HBs Ag), hepatitis B surface antibody (HBs Ab), hepatitis B core antibody (HBc Ab), hepatitis C virus antibodies (HCV Ab) will be tested at screening (V1). In case of results showing HBs Ag (negative) and HBc Ab (positive), an hepatitis B virus (HBV) deoxyribonucleic acid (DNA) testing will be performed and should be confirmed negative prior to randomization. In case of results showing HCV Ab (positive), an HCV ribonucleic acid (RNA) testing will be performed and should be confirmed negative prior to randomization.
 - **HIV screen:** Anti-HIV-1 and HIV-2 antibodies will be tested at Visit 1

- Urinalysis:
 - **Urinalysis** will include specific gravity, pH, glucose, ketones, blood, protein, nitrate, leukocyte esterase, urobilinogen and bilirubin. In case the urine dipstick test result is abnormal, a urine sample should be sent into the central laboratory for microscopic and macroscopic examination
- Vital signs: Pulse rate (beats per minute), systolic and diastolic blood pressure (mmHg) in a semi-supine or sitting position after 5 minutes, weight, respiratory rate (breaths per minute), temperature (degrees Celsius) and height (screening only)
- ECG variables: Heart rate, PR, QRS, QT, and QTc intervals after 10 minutes of rest in the supine position

Data below the lower limit of quantitation/detection limit (LLOQ) will be replaced by half of the LLOQ, data above the upper limit of quantification will be replaced by ULOQ value.

Quantitative analyses

For all laboratory variables and vital signs variables above, descriptive statistics for results and changes from baseline will be provided for each analysis window, the last value and the worst value during the on-treatment period. These analyses will be performed using central measurements only (when available) for laboratory variables.

For all parameters, mean changes from baseline with the corresponding standard error will be plotted over time.

Analyses according to PCSA

Potentially clinically significant abnormality (PCSA) analyses will be performed based on the PCSA list currently in effect at Sanofi at the time of the database lock. For parameters for which no PCSA criteria are defined, similar analyses will be done using the normal range, if applicable.

Analyses according to PCSA will be performed based on the worst value during the treatment-emergent period, using all measurements (either local or central, either scheduled, nonscheduled or repeated).

For laboratory variables, vital signs and ECG variables above, the incidence of participants with at least one PCSA during the treatment-emergent period will be summarized regardless of the baseline level and according to the following baseline status categories:

- Normal/missing
- Abnormal according to PCSA criterion or criteria

Additional analyses for suspect drug-induced liver injury

The following additional analyses will be performed for drug-induced liver injury:

- Time to onset of the initial ALT or aspartate aminotransferase (AST) elevation ($>3 \times \text{ULN}$) and total bilirubin elevation ($>2 \times \text{ULN}$) during the treatment-emergent period will be analyzed using Kaplan-Meier method.

- A graph of the distribution of peak values of ALT versus peak values of total bilirubin during the treatment-emergent period will be provided.
- For each liver function test (eg, ALT), participants having a PCSA (eg, ALT >5 ULN) will be summarized using the following categories: Returned to baseline PCSA status (or returned to value \leq ULN in case of missing baseline) before last IMP dose, Returned to baseline PCSA status after last IMP dose, Never returned to baseline PCSA status, No assessment after elevation. This summary will be performed by categories of elevation (ALT >3, >5, >10, >20 ULN).

4.8 OTHER ANALYSES

4.8.1 PK analyses

Pre-dose dupilumab concentrations in serum at Visit 2 (Day 1), dupilumab trough levels at Week 12, Week 24/EOT and post-treatment dupilumab concentrations in serum at Week 36 will be provided.

Concentrations of dupilumab (SAR231893; REGN668) in serum will be summarized in the PK population using arithmetic and geometric means, SD, standard error of the mean (SEM), coefficient of variation (CV), minimum, median and maximum per sampling time. If date and/or time of the drug injection and/or sampling is missing then the concentration will not be taken into account. For drug-treated participants, where concentration values are below the lower limit of quantification (LLOQ), one-half of the LLOQ will be used. Values will be expressed in the tables with no more than three significant figures. For participants in the placebo group, concentration values are below the LLOQ will be taken into account with a concentration in serum considered equal to 0.

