Photographs CSU representative area for commercial activities (at selected sites in selected countries)		X	X	X	X	For participants (except pediatric participants in Studies A and B and all Study C participants) who decide to participate and provide consent for the photography, photographs will be taken of a representative area of CSU involvement for commercial activities. Instructions for taking the photographs are provided in the photography reference manual.

Abbreviations: AAS7 = angioedema activity score over 7 days; ADA = anti-drug antibodies; AE = adverse events; CDLQI = children's dermatology life quality index; CU-Q2oL = chronic urticaria quality of life questionnaire; DLQI = dermatology life quality index; DNA = deoxyribonucleic acid; ECG = electrocardiogram; eCRF = electronic Case Report Form; EOS = End of study; EOT = End of treatment; EQ-5D 5L = 5-level EuroQol 5-dimensional questionnaire; EQ-5D-Y = EuroQol 5-dimensional questionnaire youth; HBc Ab = hepatitis B core antibody; HBs Ab = hepatitis B surface antibody; HCV Ab = hepatitis C virus antibodies; HIV = Human Immunodeficiency Virus; HSS7 = hives severity score over 7 days; IgE = immunoglobulin E; IMP = investigational medicinal product; ISS7 = weekly itch severity score; IVRS = interactive voice response system; IWRS = interactive web response system; OCS = oral corticosteroids; PGIC = patient global impression of change; PGIS = patient global impression of severity; PK = pharmacokinetic; q2w = every 2 weeks; RNA = ribonucleic acid; SAE = serious adverse event; SC = subcutaneous; TB = tuberculosis; UAS7 = urticaria activity score over 7 days; UCT = urticaria control test; Ur = urine.

- a Randomization/baseline Visit is defined as Day 1. All assessments at Visit 2 (Day 1) are to be conducted pre-IMP dose with the exception of the assessment of local tolerability of subcutaneous (SC) injections.
- b Participants who discontinue the study treatment prematurely (prior to completing the 24-week treatment period) will perform the EOT assessments at the time of discontinuation to assure a complete clinical assessment in close temporal proximity to the premature termination of study treatment. In addition, to allow assessment of participant outcomes over the stipulated study period, participants will be asked and encouraged to complete all remaining study visits and participate in all assessments according to the visit schedule.

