3 ANALYSIS POPULATIONS

The following populations for analyses are defined:

Table 3 - Populations for analyses

| Population | Description |
|-------------------------|--|
| Screened | All participants who sign the ICF |
| Randomized | All participants from the screened population who have been allocated to a randomized intervention by IRT regardless of whether the treatment kit was used or not. Participants treated without being randomized will not be considered randomized and will not be included in any efficacy population. |
| Intent-to-treat (ITT) | All randomized participants analyzed according to the intervention group allocated by randomization. |
| Safety | All participants randomly assigned to study intervention and who take at least 1 dose of study intervention. Participants will be analyzed according to the intervention they actually received. Randomized participants for whom it is unclear whether they took the study medication will be included in the safety population as randomized. For participants who accidentally receive a different intervention from that which was planned, the actual intervention allocation for as-treated analysis will be the dupilumab group. The pharmacodynamic (PD) analyses will be performed on the safety population. |
| Pharmacokinetic (PK) | The PK population includes all participants in the safety population with at least one non-missing result for functional dupilumab concentration in serum after first dose of the study intervention. Participants will be analyzed according to the intervention actually received. |
| Antidrug antibody (ADA) | ADA population includes all participants in the safety population who have at least one non-missing ADA result after first dose of the study intervention. Participants will be analyzed according to the intervention actually received. |

Abbreviations: ADA = antidrug antibody; ICF = Informed consent form, IRT = Interactive response technology; PD = Pharmacodynamic

Participants exposed to study intervention without being randomized will not be considered randomized and will not be included in any analysis population. The safety experience of these participants will be reported separately.

Randomized participants for whom it is unclear whether they took the study intervention will be considered exposed and will be included in the safety population as randomized.

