4.8.2.1 Association of Immunogenicity with Exposure, Safety and Efficacy

The safety and efficacy analysis mentioned below will be conducted using the following categories:

ADA positive participants: Participants with treatment-emergent or treatment-boosted response.

ADA negative participants: Participants with pre-existing immunoreactivity or negative in the ADA assay at all time points.

Impact of ADA on PK profile

Potential associations between ADA variables (eg, ADA peak titers, neutralizing antibody status, treatment-emergent, persistent, indeterminate and transient response, treatment-boosted) and impact on serum concentration profile of dupilumab may be explored. Plot of concentration of functional dupilumab in serum versus visit will be provided by ADA variables for each dupilumab dose group. Individual participant plots of dupilumab concentration according to ADA status will be provided.

Impact of ADA on clinical efficacy endpoints

Associations between the ADA variables (eg, ADA peak titers, neutralizing antibody status, treatment-emergent, persistent, treatment-boosted) and the primary efficacy endpoint may be explored for the dupilumab dosed group.

Association of ADA with clinical safety endpoints

Association of safety versus ADA status may be analyzed in the ADA population. The safety assessment may focus on the following events:

- Severe injection site reactions last longer than 24 hours or serious injection site reactions,
- Hypersensitivity reactions (SMQ (20000214) hypersensitivity narrow search confirmed by medical review),
- Anaphylactic reactions (SMQ (20000021) anaphylactic reaction narrow search).

Associations between ADA variables (eg, ADA peak titers, neutralizing antibody status, treatment-emergent, persistent and treatment-boosted) and safety may be explored.

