For the pharmacokinetics/pharmacodynamics variables summary, the reference date for the derivation of relative days of measurements will be the date of first IMP administration if the participant is treated with study intervention, or the randomization date if the participant is not treated. Pharmacokinetics /pharmacodynamics variables will be summarized by the analysis window defined in [Table 12](#) for the by visit descriptive analyses. All available values of measurements will be assigned to the appropriate visit window. In the event of multiple measurements of the same test in the same window, the one closest to the targeted visit date will be used for the by-visit summary. If they are at the same number of days away from the target day, the latest one will be used. For procedures planned on Visit 2, if it is done on the same date as the first IMP injection but the performance time is missing, it will belong to Visit 2 time window.

Table 12 - Time window for pharmacokinetics/pharmacodynamics variables

| Visit | Target Day | Serum dupilumab, ADA, Total IgE | Skin biopsy (substudy) | Basophil activation (substudy) |
|-------------------|------------|---------------------------------|------------------------|--------------------------------|
| Visit 1 | -28 to -14 | | | |
| Visit 2 (Week 0) | 1 | <1- | <1- | <1- |
| Visit 3 (Week 12) | 85 | 1+-126 | | 1+-126 |
| Visit 4 (Week 24) | 169 | 127-210 | >1+ | >126 |
| Visit 5 (Week 36) | 253 | >210 | | |

1-: up to 1st dose date/time or randomization if participant is not treated; 1+: after 1st dose date/time or randomization date if participant is not treated;

Unscheduled visits

Unscheduled visit measurements of laboratory data, vital signs and ECG will be used for computation of baseline, the last on-treatment value, analysis according to PCSAs, and the shift summaries for safety. They will also be included in the by-visit summaries if they are re-allocated to scheduled visits. Unscheduled visit measurements for efficacy data will be included in the by-visit summaries if they are re-allocated to scheduled visits.

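### The Study C PK summary calls Week 12 and Week 24 concentrations trough levels but sets no condition on dosing status, so samples from participants who have stopped dupilumab can enter the trough table and the concentration-by-ADA plots.

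*SAP*

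**What the plan says.** Study C SAP 4.8.1 describes the Week 12 and Week 24/EOT concentrations as troughs and only the Week 36 concentrations as post-treatment: "dupilumab trough levels at Week 12, Week 24/EOT and post-treatment dupilumab concentrations in serum at Week 36 will be provided". They are summarised in the PK population by arithmetic and geometric mean, SD, SEM, CV, minimum, median and maximum. Two handling rules follow:

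- Low values in the active arm are kept in the summary: "where concentration values are below the lower limit of quantification (LLOQ), one-half of the LLOQ will be used".
- There is a single exclusion, which concerns dates and times only: "If date and/or time of the drug injection and/or sampling is missing then the concentration will not be taken into account".

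The PK population in SAP section 3 is not tied to dosing status: "The PK population includes all participants in the safety population with at least one non-missing result for functional dupilumab concentration in serum", the result being after the first dose. SAP Appendix 4 (5.4) assigns samples by study day. "All available values of measurements will be assigned to the appropriate visit window": after the first dose to Day 126 for Week 12 (target Day 85), and Days 127 to 210 for Week 24 (target Day 169). If a window holds more than one sample, "the one closest to the targeted visit date will be used for the by-visit summary".

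On attendance after stopping, footnote b of the Protocol 1.3 schedule asks for EOT assessments at discontinuation and adds that "participants will be asked and encouraged to complete all remaining study visits and participate in all assessments according to the visit schedule". That schedule has serum PK at Weeks 12 and 24.

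For immunogenicity, SAP 4.8.2.1 states: "Plot of concentration of functional dupilumab in serum versus visit will be provided by ADA variables for each dupilumab dose group".

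**The concern.** A trough is a concentration at the end of a dosing interval in someone still being dosed. For a participant who continues, the scheduled samples fit: the protocol orders sampling before dosing, and the last planned q2w dose is at Week 22, two weeks before the Week 24 sample. For a participant last dosed at Week 4 who attends at Week 24, the sample is 20 weeks after dosing. Under the stated rules it still goes into the Week 24 trough summary.

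The SAP has the concept needed to avoid this. Section 4.1 defines an on-treatment period, and 4.8.2 derives ADA incidence on treatment as well as over the whole study. Neither restriction reaches the PK table or the concentration-by-ADA plots.

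At stake is the description of exposure in Study C. A reader would take the table as the exposure achieved by the assigned regimen. In the ADA plots, a low concentration caused by stopping could be read as ADA-driven clearance.

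**Working it through.** The plan gives no PK figure to reproduce. The check has two parts: whether the rules let off-drug values through, and how large the effect could be.

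**1. Tracing one participant.** Suppose IMP is stopped and the EOT sample is drawn on Day 140, and the participant also attends on Day 169. Both samples fall in the Day 127 to 210 window. Their distances from target are 169 − 140 = 29 days and 0 days, so the later, off-drug sample is used. Its dates are known, so the missing-date exclusion does not apply. Nothing in sections 3, 4.8.1 or 5.4 removes it.

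**2. When values reach half the LLOQ.** Protocol 4.2 bases the 12-week follow-up on the time for levels to fall below the LLOQ in most participants. On that timeline, full washout at Week 24 needs a last dose at about Week 12 or earlier. At Week 12 it would need someone who received only the Day 1 dose.

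**3. Effect on the Week 24 geometric mean.** Let f be the share of dupilumab-arm Week 24 samples that are off drug, and R the on-drug trough divided by LLOQ/2. The assay table is redacted, so R = 100 to 2000 is an assumption.

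If all off-drug samples are fully washed out, the ratio to the on-drug value is R^(−f):

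- f = 5%: 100^(−0.05) = 0.79; 2000^(−0.05) = 0.68.
- f = 10%: 100^(−0.10) = 0.63; 2000^(−0.10) = 0.47.

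More realistically, spread the last dose evenly over Weeks 0, 2, …, 20 (11 values), with log-linear decline from trough at 2 weeks after dosing to the LLOQ at 12 weeks. At Week 24, seven of the 11 are at LLOQ/2. The other four, at 10, 8, 6 and 4 weeks after dosing, have completed 0.8, 0.6, 0.4 and 0.2 of the decline, which sum to 2.0. The mean log ratio is

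−[7 ln R + 2(ln R − ln 2)]/11 = −(9 ln R − 2 ln 2)/11.

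This is −3.64 for R = 100 and −6.09 for R = 2000. The geometric-mean ratio is exp(f × that value):

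| Off-drug share f | R = 100 | R = 2000 | Geometric mean low by |
|---|---|---|---|
| 5% | 0.834 | 0.737 | 17% to 26% |
| 5.3% | 0.826 | 0.726 | 17% to 27% |
| 10% | 0.695 | 0.544 | 30% to 46% |

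The 5.3% row is 10% stopping with half attending: 0.05/(0.90 + 0.05). With 75 per arm, 5% is about 4 samples and 10% is 7.5.

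**4. Other statistics.** Under even stopping the arithmetic-mean ratio is about 0.95 at f = 5% and 0.90 to 0.91 at f = 10%. If all off-drug values lie below the median and the on-drug log-SD is 0.5 (assumed), the median ratio is exp(0.5 × Φ⁻¹[(0.5 − f)/(1 − f)]), which is 0.97 and 0.93.

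**5. ADA plots.** In an assumed ADA-positive group of five with one washed-out stopper, the geometric-mean ratio is R^(−1/5), or 0.40 to 0.22; the arithmetic-mean ratio is 0.80.

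**The case against.** The strongest reply is that this is a descriptive table with no test or decision attached. The endpoint is functional concentration and PK profile, and the geometric mean is only one of its summaries. The median is reported beside it and hardly moves, and a few half-LLOQ values would show in the minimum and CV. The word trough already implies end-of-interval sampling, and the dates needed to spot off-dose samples are required. Individual concentration plots by ADA status are planned, and population PK may be reported separately. All of this stands, and it limits the importance of the point. It does not change what the table will contain if the rules are followed as written.

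Four stronger readings are tempting and are not supported:

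- **That exposure will be understated by a known amount, with 10% of samples off drug.** The 10% in Protocol 9.2 is a sample-size dropout allowance. Participants who leave give no Week 24 sample, and Protocol 7.1.1 allows phone contact instead of a visit in exceptional cases.
- **That Week 12 is affected as much as Week 24.** Step 2 shows that full washout hardly applies there.
- **That the bias can only be downward.** If a stopper does not return, the EOT sample taken at discontinuation may fill the window. It may be mid-interval and above trough.
- **That the ADA plots are confounded.** This needs stopping to differ by ADA status. It is plausible, because IMP-related allergic reactions requiring treatment force discontinuation (Protocol 7.1.1) and the SAP relates hypersensitivity to ADA. No data in the documents show it.

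**Conclusion.** The point holds as a gap in the Study C PK rules: following them puts off-drug concentrations into a summary labelled trough and into the concentration-by-ADA plots. Washed-out values lower the summary relative to the on-drug trough, chiefly the Week 24 geometric mean. The size cannot be determined from the documents. The illustrative figures in step 3 depend on the assumed off-drug share, on R, on evenly spread stopping and on log-linear decline to the LLOQ at 12 weeks. For the ADA plots the documents support a conditional risk only. Primary, key secondary and safety conclusions do not depend on this, so it is a worthwhile low-cost improvement. The Study A and Study B SAPs carry the same rule in their own section 4.8.1.

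**What to change.** In Study C SAP 4.8.1 and 4.8.2.1, state that the Week 12 and Week 24 trough summaries and the ADA-versus-concentration plots use only samples whose time since the most recent IMP dose is consistent with the end of the assigned dosing interval (q2w or q4w). The tolerance should cover both the ±3-day dosing window (Protocol Table 3) and the ±3-day treatment-period window (Protocol 4.1). On the upper side that is 14 + 3 + 3 = 20 days for q2w and 28 + 3 + 3 = 34 days for q4w. List or summarise all other post-dose samples separately, by time since last dose.

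Reusing the on-treatment period of SAP 4.1 (last IMP + 14 days, or + 28 days for children under 30 kg) would not be enough, even with 3 days added. It could drop valid samples from completers, since a q2w sample can fall 20 days after dosing. It would also keep mid-interval EOT samples, and samples taken after missed doses in participants who later resume; Protocol 7.1.2 requires permanent discontinuation only after more than two consecutive missed doses.

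The cost is a sentence in each section and a programming filter on dates that 4.8.1 already requires. The downside is slightly fewer samples in the trough table.
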